8.5.1.4. Anomalous Values

If a value is considered to be anomalous due to being inconsistent with the expected PK profile, it may be appropriate to exclude this point from the PK analysis. However, the exclusion of data must have strong justification and will be documented in the raw data and CSR.

Embedded BLQ values may be considered anomalous depending on the route of administration and the characteristics of the drug.

Positive predose values >5% of C_{max} may be excluded from the summary statistics and statistical analysis at the discretion of the Pharmacokineticist.

8.5.2. Presentation of Pharmacokinetic Data

8.5.2.1. Presentation of Pharmacokinetic Concentration Data

The following rules will be applied if there are values that are BLQ or if there are missing values (eg, no result [NR]) in a plasma concentration data series to be summarized.

- For the calculation of summary statistics, BLQ values will be set to zero.
- If an embedded BLQ value is considered anomalous within the concentration-time profile, this value will be excluded from the summary statistics.
- Where there is NR, these will be set to missing.
- If there are fewer than 3 values in the data series, only the minimum, maximum, and n will be presented. The other summary statistics will be denoted as not calculated (NC). A BLQ is considered a value.
- If all the values are BLQ, then the arithmetic mean, arithmetic standard deviation (SD), median, minimum, and maximum will be presented as zero, and the geometric mean and geometric coefficient of variation (CV) will be denoted as NC.
- If the value of the arithmetic mean or median is BLQ, it will be presented as zero and the geometric mean and geometric CV will be denoted as NC.

8.5.2.2. Presentation of Pharmacokinetic Parameters

For the calculation of summary statistics of PK parameters, all NR and NC values in a data series will be set to missing.

The AUC values will be set to NC if they have been calculated using fewer than 3 concentrations, and/or 3 concentrations if the last is C_{max} .

8.5.3. Pharmacokinetic Statistical Methodology

All PK concentrations and parameters will be listed.

Descriptive statistics (mean, median, minimum, maximum, SD, geometric mean, and geometric CV) will be calculated for all PK parameters for GDC-9545.

Summary tables, mean (+ SD) figures, overlaying individual figures, and individual figures by treatment and time postdose will be provided for plasma PK concentrations. All figures will be produced on both linear and semi-logarithmic scales. The +SD bars will only be displayed on the linear scale.

Summary tables by treatment will be provided for all PK parameters, with the exception of regression diagnostic PK parameters.

The PK parameters C_{max} , AUC_{0-t} , and $AUC_{0-\infty}$ for GDC-9545 will be analyzed to evaluate the relative bioavailability of GDC-9545 as a Phase 3 capsule formulation compared to a Phase 1 tablet formulation under fasted conditions and to assess the food effect on GDC-9545 PK for a Phase 3 capsule formulation. The mixed-effect analysis of variance model for three-period crossover design will be used for formulation comparison and fasted state and fed state comparison of capsule. The model will include sequence, formulation, and period as fixed effects and a random effect for subject within sequence. An unstructured covariance structure will be used; however, if this fails to converge, an alternative covariance structure may be applied.

Log transformed C_{max} , AUC_{0-t} , and $AUC_{0-\infty}$ values will be evaluated to estimate ratios of geometric mean values and the corresponding 90% confidence intervals (CIs).

The comparisons of interest are:

Relative bioavailability: Treatment B, capsule (Test) vs Treatment A, tablet (Reference)

Food effect on capsule: Treatment C, fed (Test) vs Treatment B, fasted (Reference)

An example of the SAS code that will be used (assuming formulation coding is 1 = Treatment A, 2 = Treatment B and 3 = Treatment C) is as follows:

```
proc mixed data=pk;
  by parcatln parcatl pkday paramn param;
  class trtan aperiod trtseqp usubjid;
  model log_pk = trtan aperiod trtseqp / residual ddfm=kr;
  random intercept / subject=usubjid(trtseqp) type=un;
```

```
estimate `Capsule - tablet' trtan -1 1 0/ cl alpha=0.1;  
estimate `fed - fasted' trtan 0 -1 1/ cl alpha=0.1;  
run;
```

The parameter t_{max} will be analyzed nonparametrically using the Wilcoxon signed-rank test. The median difference between the test and reference investigational products and the corresponding 90% CI will be calculated.

8.6. Safety and Tolerability Assessments

8.6.1. Adverse Events

All AEs will be coded using the Medical Dictionary for Regulatory Activities Version 22.1 (or higher if upversioned during the study). All AEs will be assigned severity grade using National Cancer Institute Common Terminology Criteria for Adverse Events Version 5.0 (or higher if upversioned during the study).

A treatment-emergent AE (TEAE) will be defined as an AE that starts during or after the first dose, or starts prior to the first dose and increases in severity after the first dose.

A treatment-related TEAE will be defined as a TEAE with a relationship of related to the study treatment, as determined by the investigator.

The AEs of special interest for this study are defined as follows:

- Cases of potential drug-induced liver injury that include an elevated alanine aminotransferase (ALT) or aspartate aminotransferase (AST) in combination with either an elevated bilirubin or clinical jaundice, as defined by Hy's Law
- Suspected transmission of an infectious agent by the study drug as defined below:
 - ○ Any organism, virus, or infectious particle (eg, prion protein transmitting transmissible spongiform encephalopathy), pathogenic or non-pathogenic, is considered an infectious agent. A transmission of an infectious agent may be suspected from clinical symptoms or laboratory findings that indicate an infection in a subject exposed to a medicinal product. The term applies only when a contamination of the study drug is suspected
- Grade ≥ 3 nausea/vomiting/diarrhea
- Grade ≥ 2 thromboembolic events (pulmonary embolism, deep vein thrombosis, and embolism)
- Grade ≥ 3 renal failure (including acute kidney injury or other similar medical concepts)
- Grade ≥ 3 hepatitis or elevation in ALT or AST
- Grade ≥ 2 vaginal or uterine hemorrhage
- Grade ≥ 2 bradycardia

- Any grade of endometrial cancer.

All AEs, serious AEs and AEs of special interest will be listed. In addition to the data recorded in the database, the listings will include derived onset time and duration. Onset time will be calculated from the time of the last dose for TEAEs only.

The frequency of subjects with TEAEs and the number of TEAEs will be summarized for the following categories:

- TEAEs (overall, serious, leading to discontinuation, and leading to death) by treatment
- TEAEs by severity and treatment
- Treatment-related TEAEs (overall, serious, leading to discontinuation, and leading to death) by treatment
- Treatment-related TEAEs by severity and treatment

The frequency of subjects will be summarized separately for TEAEs and treatment-related TEAEs by the following:

- System organ class, preferred term, and treatment
- Preferred term and treatment

The frequency of subjects will be summarized separately for clustered TEAEs, presenting the TEAEs by the combined preferred term and treatment by the following:

- (1) combining the preferred terms “sinus bradycardia” and “bradycardia”
- (2) combining the preferred terms “neutropenia” and “neutrophil count decreased”
- (3) combining the preferred terms “thrombocytopenia” and “platelet count decreased”
- (4) combining the preferred terms “thrombocytosis” and “platelet count increased”
- (5) combining the preferred terms “leukopenia” and “leukocyte count decreased”
- (6) combining the preferred terms “leukocytosis” and “leukocyte count increased”

For the AE data the following rules will apply:

- For the derivation of TEAE status: If the start date/time of an AE is incomplete or missing, an AE will be assumed to be a TEAE, unless the incomplete start date/time or the end date/time indicates an AE started prior to the first dose.
- For the derivation of treatment-related TEAE status: If the study treatment relationship for a TEAE is missing, a TEAE will be assumed to be a treatment-related TEAE.

- For the derivation of onset time: If the start date/time of an AE is missing, onset time will not be calculated. If the start date/time of an AE is incomplete, where possible, the minimum possible onset time will be calculated and presented in ‘≥DD:HH:MM’ format (eg, if the date/time of the last dose is 01MAY2019/08:00 and recorded start date/time of an AE is 03MAY2019, then the minimum possible onset time will be calculated by assuming the AE started at the first hour and minute of 03MAY2019 [03MAY2019/00:00], thus will be presented as onset time ≥01:16:00 in the listing).
- For the derivation of duration: If the end date/time of an AE is missing, duration will not be calculated. If the start or end date/time of an AE is incomplete, where possible, the maximum possible duration will be calculated and presented in ‘≤DD:HH:MM’ format (eg, if the start of an AE date/time is 01MAY2019/08:00 and its recorded end date/time is 03MAY2019, then the maximum possible duration will be calculated by assuming the AE ended at the last hour and minute of 03MAY2019 [03MAY2019/23:59], thus will be presented as duration ≤02:15:59 in the listing).
- For the calculation of summary statistics: If the severity of a TEAE is missing, a TEAE will be counted under the maximum severity possible.
- For the calculation of summary statistics: If a subject experienced multiple TEAEs with the same preferred term for the same treatment, this will be counted as 1 TEAE for that treatment under the maximum severity recorded.

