8.2.3 ASSESSMENT OF SEVERITY OF ADVERSE EVENTS

The AE severity grading scale for the NCI CTCAE (version 5.0) will be used for assessing AE severity. Table 8-1 will be used for assessing AE severity for AEs that are not specifically listed in the NCI CTCAE.

Table 8-1 Adverse Event Severity Grading Scale for Events Not Specifically Listed in NCI CTCAE

Grade	Severity
1	Mild; asymptomatic or mild symptoms; clinical or diagnostic observations only; or intervention not indicated
2	Moderate; minimal, local, or non-invasive intervention indicated; or limiting age-appropriate instrumental activities of daily living ^a
3	Severe or medically significant, but not immediately life-threatening; hospitalization or prolongation of hospitalization indicated; disabling; or limiting self-care activities of daily living ^{b,c}
4	Life-threatening consequences or urgent intervention indicated ^d
5	Death related to adverse event ^d

NCI CTCAE=National Cancer Institute Common Terminology Criteria for Adverse Events.

Note: Based on the most recent version of NCI CTCAE (v5.0), which can be found at: http://ctep.cancer.gov/protocolDevelopment/electronic_applications/ctc.htm

^a Instrumental activities of daily living refer to preparing meals, shopping for groceries or clothes, using the telephone, managing money, etc.

^b Examples of self-care activities of daily living include bathing, dressing and undressing, feeding oneself, using the toilet, and taking medications, as performed by subjects who are not bedridden.

^c If an event is assessed as a “significant medical event,” it must be reported as an SAE (see [Section 8.4.2](#) for reporting instructions), per the definition of SAE in [Section 8.1.2](#).

^d Grade 4 and 5 events must be reported as SAEs (see [Section 8.4.2](#) for reporting instructions), per the definition of SAE in [Section 8.1.2](#).

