8.1.1. Calculation of the Summary Statistics

For continuous data the following rules will be applied:

- Missing values will not be imputed, unless specifically stated otherwise.
- Unrounded data will be used in the calculation of summary statistics.
- If the number of subjects with valid observations (n) < 3 , summary statistics will not be calculated, with the exception of n , minimum, and maximum.
- As Early Termination data is not associated with any scheduled timepoint, it will be excluded from all calculations of summary statistics.

For categorical data the following rules will be applied:

- If the categories of a parameter are ordered (eg, AE severity), all categories between the possible minimum and maximum categories will be included, even if $n = 0$ for a given category. If the categories are not ordered (eg, race), only those categories for which there is at least 1 subject represented will be included.
- Missing values will not be imputed, with the exception of AEs where the ‘worst-case’ approach will be taken (see [Section 8.6.1](#)), or unless specifically stated otherwise. A ‘missing’ category will be included for any parameter for which information is missing. This will ensure that the population size totals are consistent across different parameters.

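### On its plain reading, the SAP 8.6.1 rule for missing severity puts a non-fatal ungraded TEAE in the Grade 5 (death) row

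*SAP*

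**What the plan says.** The SAP (8.6.1) sets the severity scale: "All AEs will be assigned severity grade using National Cancer Institute Common Terminology Criteria for Adverse Events Version 5.0". The protocol (8.2.3) agrees: "The AE severity grading scale for the NCI CTCAE (version 5.0) will be used for assessing AE severity". For events that CTCAE does not list, Protocol Table 8-1 defines Grades 1 to 5. Grade 5 reads "Death related to adverse event", and a footnote to the table requires Grade 4 and 5 events to be reported as SAEs.

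The general rule for categorical data (SAP 8.1.1) is: "Missing values will not be imputed, with the exception of AEs where the ‘worst-case’ approach will be taken". For other parameters with missing information, the same section adds a missing category to the table. For ordered categories, with AE severity as its example, "all categories between the possible minimum and maximum categories will be included", even when a category is empty.

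The specific rule is in SAP 8.6.1: "If the severity of a TEAE is missing, a TEAE will be counted under the maximum severity possible".

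The affected summary is "TEAEs by severity and treatment", together with its treatment-related counterpart. Fatal outcomes are counted separately, under "TEAEs (overall, serious, leading to discontinuation, and leading to death) by treatment". A missing relationship is imputed as related.

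**The concern.** A worst-case rule does little harm when the top category is merely severe. On a five-grade scale the top category is an outcome, death, and the outcome is recorded separately from the grade. Assigning that category to an event known to have resolved contradicts data already in the database.

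Incidence and severity of AEs are a secondary endpoint (Protocol 3.3, SAP 3.2) and are summarised by treatment. In a study of healthy volunteers, a Grade 5 entry that reflects only a blank field would have to be explained in the study report. It would also disagree with the report's own counts of deaths and SAEs.

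**Working it through.** The plan gives no figure to reproduce, so the check is mainly a reading of the rules side by side, followed by simple proportions.

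1. **Top of the scale.** Protocol 8.2.3 and SAP 8.6.1 both use CTCAE v5.0. Table 8-1, the only place where the documents define the grades, ends at Grade 5 = death.
2. **Meaning of 'possible'.** SAP 8.1.1 applies the word to the minimum and maximum categories of an ordered scale and names AE severity as the example. The table therefore has a Grade 5 row, and the maximum severity possible is, on its face, Grade 5.
3. **Any limit from other data.** The SAP 8.6.1 rule for TEAE status has one: the event is assumed treatment-emergent unless its dates show otherwise. The severity rule has no comparable condition on outcome or seriousness. The bullet after it, on repeated events, uses the maximum severity *recorded*, a different term.
4. **Any other destination.** SAP 8.1.1 makes AEs the exception to its no-imputation rule, so the missing category used for other parameters does not catch the event.
5. **Tables reached.** The event enters TEAEs by severity. It also enters treatment-related TEAEs by severity if relatedness is yes or missing. It does not enter the serious or leading-to-death counts, which are separate categories.
6. **Size, given one ungraded non-fatal TEAE under a treatment.** Inputs are 18 enrolled and a minimum of 12 completers (Protocol 4.1 and 9.6), each subject receiving all three treatments by design.
   - All 18 received the treatment: 1/18 = 5.6% apparent Grade 5 incidence.
   - Only 12 received it: 1/12 = 8.3%.
   - Correct value in either case: 0/18 or 0/12 = 0%.
7. **After the change.** With a cap by outcome, or a missing row, the same event adds 0 to Grade 5 instead of 1.

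**The case against.** The strongest counter-argument is the wording of the neighbouring bullets. For partial dates, SAP 8.6.1 speaks of a minimum possible onset time and a maximum possible duration, and there 'possible' means compatible with what was recorded. Read that way, a resolved event cannot be Grade 5. This is a fair alternative reading and it stands as such. However, the severity bullet does not say it, and SAP 8.1.1 uses the word for the full scale of this same variable.

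Other points carry weight:

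- Table 8-1 formally covers only events that CTCAE does not list. If 'possible' meant possible for the particular term, the documents do not show that Grade 5 is available for every listed term.
- Protocol 8.1.2 describes severity loosely as mild, moderate or severe. That is an illustration of severe versus serious; the grading scale is set in 8.2.3.
- The detailed table layouts are in the TFL shells, which are not among the documents and may carry footnotes.
- Protocol 8.2 requires the investigator to assess severity for every recorded AE. With one site, 18 subjects and confinement to Day 8 of each period, a grade still missing at lock should be rare.
- The duty to report Grade 4 and 5 events as SAEs falls on the investigator. An imputation made only for a summary table does not breach it.

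A reader might infer that the report would state that a subject died, or that a false fatal entry is to be expected. The documents support neither. Deaths are counted in a separate category that would correctly show zero, all AEs are listed so the event can be traced, and nothing suggests that ungraded events are likely.

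**Conclusion.** The point holds as a defect of wording with a limited effect. On the plain reading, the rule assigns Grade 5 to an ungraded TEAE regardless of outcome. In the rare case where it is triggered, the severity tables would contradict the leading-to-death count and the SAE data. The apparent Grade 5 incidence of 5.6% to 8.3% for a treatment is conditional on one such event; it is not an expected bias. This rests on two assumptions: that 'possible' refers to the whole scale, as in SAP 8.1.1, and that the TFL shells do not override it. The effect stays within descriptive secondary safety tables: SAP 8.6.6 plans no inferential safety analysis, and the primary PK comparisons do not use AE grades. It is still worth correcting before database lock, because the rule exists only for this residual case and the repair is small.

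**What to change.** Replace the severity sentence in SAP 8.6.1 with text such as:

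*If severity is still missing after query, the TEAE will be counted under the highest grade compatible with its recorded outcome and seriousness (Grade 5 only if the outcome is fatal; Grade 4 only if recorded as life-threatening or urgent intervention was indicated; otherwise Grade 3), and imputed grades will be footnoted and not used to derive AESI status.*

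The Grade 4 condition follows both limbs of Table 8-1. The AESI clause is needed because several AESI definitions start at Grade 2 or 3, so an imputed Grade 3 would cross them by default.

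Alternatively, show ungraded TEAEs in a separate missing row, as SAP 8.1.1 already does for other categorical parameters. This avoids counting a trivial event as severe, but the general worst-case statement in SAP 8.1.1 would need a matching edit.

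The cost of the replacement text is one SAP sentence and one more line in the ADaM derivation, with no protocol amendment. The imputation becomes slightly less conservative.

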8.6.2. Clinical Laboratory Parameters

All clinical laboratory parameters, with changes from period specific baseline, will be listed; any value outside the clinical reference range will be flagged. Separate listings will be provided for any parameter for which there is any individual subject value outside the respective clinical reference range.

Summary tables and boxplots by treatment and timepoint will be provided for clinical chemistry and complete blood count parameters, with changes from period specific baseline.

Values recorded as <x, ≤x, >x, or ≥x will be displayed in the listings as recorded. For the derivation of listing flags, calculation of summary statistics, and presentation in the figures, <x and ≤x values will be set to half of x, whereas >x and ≥x values will be set to x.

8.6.3. Vital Signs Parameters

All vital signs parameters, with changes from period specific baseline, will be listed; any value outside the clinical reference range will be flagged.

Summary tables and boxplots by treatment and timepoint will be provided for all vital signs parameters, with changes from period specific baseline.

8.6.4. 12-lead Electrocardiogram Parameters

All 12-lead ECG parameters, with changes from period specific baseline, will be listed; any value outside the clinical reference range will be flagged.

Summary tables and boxplots by treatment and timepoint will be provided for all 12-lead ECG parameters, with changes from period specific baseline.

8.6.5. Other Assessments

Medical history and surgical and procedure history will be listed.

All other safety and tolerability assessments not detailed in the above sections will be listed only.

8.6.6. Safety and Tolerability Statistical Methodology

No inferential statistical analyses are planned.

9. INTERIM ANALYSES

No interim analyses are planned.

10. SIGNIFICANT CHANGES FROM THE PROTOCOL-SPECIFIED ANALYSES

There were no significant changes from the protocol-specified analyses.

